7.6 Correlative Studies

We will collect blood samples at regular intervals (See Section 4.2) to facilitate monitoring immune responses, such as DC expansion and maturation. We will also follow T-cell inducible costimulator (ICOS) expression. ICOS is a member of the immunoglobulin superfamily. Responses to immunotherapy have been associated with increased ICOS expression on CD8+ T-cells, particularly following CTLA-4 blockade¹⁰⁸⁻¹¹¹. We will follow serum levels of high-mobility group box 1 (HMGB1), whose release has been linked to antitumor immune responses^{112,113}. Flow cytometry will be performed to track measures of DC maturation such as CD83 and CD86 expression¹¹⁴. Other correlative studies will be performed in collaboration with [name] laboratory and the study sponsor. Details regarding blood processing for peripheral blood mononuclear cell (PBMC) isolation are shown in the Appendix.

Due to potential transient lymphocytic effects of the SARS-CoV2 vaccine, correlative blood should not be drawn within a 5-day period after administration.

Testing for anti-drug antibody (ADA) and CDX-1140 pharmacokinetics will be performed at baseline and prior to, two hours after, and one day after each CDX-1140 infusion. These tests will be performed at Celldex Lab in Fall River, MA. Approximately 10 mL of blood will be collected in serum-separating tubes (SST). After clotting at room temperature for 30 minutes, the samples will be spun at 3000 RPM at 4°C for 15 minutes. Plasma will be aliquoted into 3-4 cryovials and frozen -80°C. Study samples will be shipped to Celldex at convenient intervals or at Celldex's request.

8.0 STATISTICAL CONSIDERATIONS

8.1 Randomization Procedure

At the time of study registration, subjects will be stratified by EGFR/ALK mutation status and disease burden and then will be randomized 1:1 between the two study arms using a modified permuted block treatment allocation scheme¹¹⁵. Block sizes of 2 (65%) and 4 (35%) will be considered. Study subjects and study personnel will NOT be blinded with respect to the randomization result.

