4.1 General Design

This is a randomized, open-label phase I/II study. Subjects will be randomized in a 1:1 ratio to receive FLT3 ligand, anti-CD40 antibody, and SBRT (Arm 1) versus standard care (Arm 2). Subjects on either study arm with limited disease will receive SBRT to all evident sites of active disease. Subjects on Arm 1 with extensive disease will initially receive SBRT to a single site of disease but may receive additional “cycles” of FLT3 ligand, anti-CD40 antibody, and SBRT at later time points. Subjects on Arm 2 with extensive disease are expected to receive some form of standard systemic therapy (e.g., docetaxel). Subjects on Arm 2 with limited disease may also receive standard systemic therapy following completion of SBRT to all sites of evident disease, at the discretion of the treating physicians. All subjects will be followed closely for treatment-related toxicities. Whole-body PET/CT and CT imaging will be performed prior to study entry, and restaging CT will be performed every 8 weeks thereafter.

In the phase I component of this study, subjects will be randomized between study arms until 6 subjects have been randomized to Arm 1. Study accrual will then be halted until 8 weeks after the last study subject begins treatment.

If the pre-specified safety criteria are achieved in the Phase I portion of this study, the study will proceed to phase II. The total sample size (Phase I and Phase II) will be 46 subjects. All 46 subjects will be included in efficacy analyses.

If the pre-specified safety criteria are not achieved in the Phase I portion of this study, the investigators and Celldex will review safety data from this trial as well as other trials using CDX-301 and CDX-1140 and determine if the experimental treatment regimen should be altered (e.g., by reducing the CDX-1140 dose). The study protocol would be amended accordingly, and Phase I component with the new treatment regimen would be added.

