5.1 Stereotactic Body Radiotherapy

5.1.1 Patient Selection – Limited v. Extensive Disease

Stereotactic body radiotherapy (SBRT) will be administered to all subjects on Arm 1 and to subjects with limited disease burden on Arm 2. For the purposes of this trial, “limited disease” is defined as disease that, in the estimation of the treating physician, can reasonably and safely be addressed in a comprehensive fashion with SBRT. This definition will generally align with recent consensus definitions of oligometastatic disease, such as having 5 or fewer active lesions⁸⁵⁻⁸⁷. Occasionally, a

study subject with 5 or fewer active lesions may be deemed to be ineligible for comprehensive SBRT due to large target size (above **7 cm for lung tumors**⁸⁸ or above **5 cm for other lesions**^{89,90}), target location adjacent to a radiosensitive normal structure, or prior radiotherapy exposure. Rarely, comprehensive SBRT a subject with 6 or more active lesions may be deemed feasible and safe (e.g., two small lung tumors, two small liver metastases, and two spine metastases). Any subject with more than 10 active lesions will be deemed to have extensive disease⁹¹.

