8.3 Phase II Primary Endpoint – Progression-free Survival

The primary study hypothesis is that treatment with FLT3 ligand, CD40 agonist antibody, and SBRT (Arm 1) will improve progression-free survival (PFS) compared to standard therapy (Arm 2). Based on published data for patients with advanced NSCLC who require treatment after several lines of standard therapy, we expect that the median PFS duration for subjects on Arm 2 will be 5 months. Based on our recent study using FLT3 ligand and SBRT and the expectation that CD40 agonist antibody will enhance treatment efficacy, we hypothesize that the median PFS duration for subjects on Arm 1 will be 10 months. This improvement is approximately equivalent to a hazard reduction of 50%. We are employing a *randomized phase II screening design*, using $\alpha = 0.20$ (wherein a p-value <0.20 indicates a positive trial). We anticipate that study accrual will take place over 24 months, and we will analyze treatment efficacy 12 months after accrual is completed. We do not expect any subjects to be lost to follow-up before the primary endpoint occurs. Based on these assumptions, our total sample size of 46 subjects yields study power of 81% using a two-sided log-rank test.

We will compare the distributions of PFS between treatment arms using a two-sided log-rank test. The rates at various timepoints (e.g., every 6 months after randomization) and median PFS durations for each arm will be estimated using the Kaplan-Meier method. Associated 95% confidence intervals (CI) will be calculated using Greenwood's formula. Cox proportional hazards models will be used to estimate the impact of study therapy on PFS duration.

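### Small printed block sizes in an unblinded, stratified trial let an informed enroller call about half of all assignments with roughly 90% accuracy, and no allocation concealment is described

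*Combined protocol and SAP*

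**What the plan says.** Section 8.1 states that "subjects will be stratified by EGFR/ALK mutation status and disease burden" and are then "randomized 1:1 between the two study arms using a modified permuted block treatment allocation scheme". Two binary factors give four strata. The sizes follow: "Block sizes of 2 (65%) and 4 (35%) will be considered". The section closes with "Study subjects and study personnel will NOT be blinded with respect to the randomization result". Section 4.1 confirms the open-label design and the total: "The total sample size (Phase I and Phase II) will be 46 subjects".

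Section 5.1.1 defines limited disease as disease that, "in the estimation of the treating physician, can reasonably and safely be addressed in a comprehensive fashion with SBRT". Some limits apply. More than 10 active lesions is always extensive (Section 5.1.1), and so is any lung tumor over 7 cm or other lesion over 5 cm (Section 5.1.4). Between those limits, a subject with five or fewer lesions may be called extensive and one with six or more may be called limited.

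The documents do not say who holds the allocation list, whether assignment is central, whether block sizes are withheld from enrolling staff, or how the permuted block scheme is modified.

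**The concern.** Varying the block size protects an open-label trial only if enrolling staff do not know the sizes. Here the sizes and their frequencies stand in the document that every enroller holds, and the smaller size dominates. Staff see each result, and in Phase I they must count Arm 1 assignments up to six (Sections 4.1 and 8.2).

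An enroller who expects the next assignment can, without any conscious intent, hurry or delay a registration. A borderline patient can also be classed into the burden stratum whose next slot looks favorable. Motive needs no misconduct: the team expects Arm 1 to do better (Section 8.3), and Arm 2 subjects cannot cross over (Section 5.2.2). Prognosis could then differ between arms, and PFS would differ with it whether or not the treatment works. The trial is called positive at p < 0.20 with 46 subjects, so a modest imbalance can matter.

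**Working it through.** **The plan's own figure.** The documents give no predictability figure. The nearest stated result is the power, "our total sample size of 46 subjects yields study power of 81% using a two-sided log-rank test". With exponential PFS, medians of 5 and 10 months, uniform accrual over 24 months and 12 months of further follow-up, the event probability is 1 − (e^(−12λ) − e^(−36λ))/(24λ). This gives 0.945 on Arm 2 and 0.788 on Arm 1, so 23 × (0.945 + 0.788) = 39.9 events. Schoenfeld power at two-sided 0.20 is 81.8%, so the planning figure reproduces. Nothing below depends on it.

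**Inputs for predictability.** Blocks of 2 (65%) and 4 (35%), 1:1, four strata, 46 subjects. Section 8.1 does not say whether 65% is a share of blocks or of subjects. I take blocks as the main case. The assumed observer knows the mix and sees all earlier assignments in the stratum.

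**Second subject in a stratum.** A block of 2 fixes the second assignment. A block of 4 gives the other arm with probability 2/3. So the chance of the other arm is 0.65 + 0.35 × 2/3 = 0.883.

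**Later subjects, order of sizes hidden.** Exact Bayesian enumeration over 12 subjects in a stratum gives these correct-guess rates:

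| Position | 1 | 2 | 3 | 4 | 5 | 6 |
|---|---|---|---|---|---|---|
| Correct | 50% | 88.3% | 55.8% | 92.4% | 53.8% | 91.0% |

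The pattern then settles. Every even-numbered position is callable with at least 88% probability, averaging about 91%. Odd positions are near chance unless one arm leads by 2 in the stratum, when the next assignment is certain. For the third subject that has probability 0.35 × 1/3 = 0.117. Over 12 subjects, 72.4% of guesses are right and 7.6% of assignments are certain.

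**Block boundaries known.** A block of 2 has 1 determined assignment, and a block of 4 has 1/3 × 2 + 2/3 × 1 = 4/3 on average. Mean block length is 0.65 × 2 + 0.35 × 4 = 2.7.
- 65% of blocks: (0.65 × 1 + 0.35 × 4/3)/2.7 = 41.4% determined.
- 65% of subjects: 0.65 × 1/2 + 0.35 × 1/3 = 44.2% determined.

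If 65% is a share of subjects, blocks of 2 make up 0.325/(0.325 + 0.0875) = 78.8% of blocks. With order hidden, the second subject is then called with 92.9% probability, about 73% of guesses are right, and 4-6% of assignments are certain.

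**Comparison with an equal mix of 4 and 6** (46 subjects in strata of 12, 12, 11 and 11; order hidden):

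| | Printed 2/4 mix | 4/6 mix |
|---|---|---|
| Callable at 75% or more | 52% | about 41% |
| Callable at 80% or more | 52% | about 31% |
| Callable at 85% or more | 52% | about 16% |
| Certain | about 8% | about 6% |
| Guesses right | 72% | 67-68% |

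**Illustration of bias.** Assume no treatment effect, a binary prognostic factor with hazard ratio 2, and P(good prognosis) = 0.5 + s(2p − 1), where p is the foreseen chance of Arm 1. The nominal chance of a false positive favoring Arm 1 is 0.20/2 = 10%. With s = 0.25 simulation gives 18-20% for the printed mix and 15-16% for 4/6 blocks. With s = 0.15 it gives 14-16% and 12-14%. With no steering it is 9-11% throughout. Neither the hazard ratio nor s has a source in the documents.

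**The case against.** A reader might infer that half of all assignments are known in advance. The documents do not support that. Known in that sense would need every block to be of size 2; the figures are about 8% with order hidden and 41-44% with boundaries known. The half that can be called is called with roughly 90% accuracy, and only by someone who tracks each stratum. Section 8.1 says that staff are unblinded, not that they keep such a record.

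Other points against:

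- The sizes are only to be considered, and the modification to the scheme is undescribed, so the actual procedure may be safer. This stands as a qualifier, but the text rules nothing out.
- The contrast of 52% with 16% uses the most favorable of the cut-offs tabulated up to 85%. At 75% it is 52% against about 41%. This stands.
- Section 8.1 places stratification before randomization, and the burden class is bounded by lesion count and size. Misclassifying a patient also changes whether comprehensive SBRT is given on either arm, which deters it. This narrows the opening; borderline patients remain.
- Section 8.4 plans multivariable PFS analyses that include disease burden and performance status, so it would be too strong to say that no analysis can help. They are exploratory, however, and cannot cover unrecorded factors.
- With 46 subjects in four strata, small blocks protect balance. That is a legitimate aim, and its loss is costed in the fix.

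**Conclusion.** The point holds as a should-fix. The plan combines mostly size-2 blocks, published sizes, unblinded staff, a partly judgmental stratum and no described concealment. An informed enroller can call about half of assignments at roughly 88-91% and would be right 72% of the time overall. This rests on the printed mix being used, on knowledge of it, and on tracking within strata.

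The existence of the risk follows from the text; the size of the resulting bias does not. The false-positive figures show what assumed steering would do and are not an estimate for this trial. Nor do the documents show that concealment will be absent in practice, only that none is described.

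**What to change.** In Section 8.1:

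1. Drop blocks of 2 and use randomly mixed blocks of 4 and 6.
2. Remove the block sizes from the protocol and hold them in a restricted randomization document. State who releases assignments.
3. Record and lock eligibility and the disease-burden stratum, with lesion count and sizes, before the assignment is released.

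The first step alone is a partial remedy, as the comparison table shows, so the second and third matter as much.

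The cost is a new list and about a paragraph of text, plus some loss of balance. Arm sizes would differ by 4 or more in about 12-13% of trials instead of 4-5%. A big-stick rule capping within-stratum imbalance at 2 would raise this to about 22%, which is why 4/6 blocks are preferred here. PFS power at 25:21 is within 1 point of that at 23:23.

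The final toxicity rule in Section 8.2 is more sensitive, because it is written for exactly 23 subjects on Arm 1. Keeping the cut-off at 4, P(X ≤ 4) from the binomial is:

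| Arm 1 number | Acceptance at 35% | Acceptance at 12.5% |
|---|---|---|
| 21 | 9.2% | 88.8% |
| 23 | 5.5% | 84.8% |
| 25 | 3.2% | 80.5% |

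The section states at most 5% and at least 85%. The rule and its operating characteristics should therefore be restated for the number actually on Arm 1.

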8.2 Phase I Primary Endpoint – Dose-Limiting Toxicity

A stopping rule for safety will be implemented as follows: After 6 subjects are randomized to Arm 1 (which will take place after approximately 12 total subjects are enrolled), accrual will be temporarily suspended for DLT monitoring. 8 weeks after the 6th subject on Arm 1 starts treatment, the study will proceed to Phase II if no more than one out of six subjects on Arm 1 has experienced a DLT (defined in Section 7.2).

If the pre-specified safety criteria are not achieved in the Phase I portion of this study, the investigators and Celldex will review safety data from this trial as well as other trials using CDX-301 and CDX-1140 and determine if the experimental treatment

regimen should be altered (e.g., by reducing the CDX-1140 dose). The study protocol would be amended accordingly, and Phase I component with the new treatment regimen would be added.

At the conclusion of the trial, study therapy will be considered safe and worthy of further study if no more than 4 out of 23 subjects on Arm 1 experience a DLT. The target Grade 3 toxicity rate is no more than 12.5%, and a toxicity rate greater than 35% is considered clinically unacceptable. This design has the following operating characteristics: The probability of accepting the treatment for further study if the true toxicity rate is unacceptably high (>35%) is at most 5%. In contrast, there is at least an 85% probability of accepting the treatment for further study if the true toxicity rate is less than 12.5%.

The proportion of patients on Arm 1 who develop a DLT will be computed, along with Clopper-Pearson 95% exact confidence intervals. Frequencies of specific treatment-related adverse events (including delayed adverse events) and event grades will be characterized using counts and percentages.

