Increases in liver function tests in the 24-48 hours following the CDX-1140 are an expected pharmacodynamic effect of the drug. The increases are usually low-grade, but can be grade 3, and liver function tests typically return to approach baseline within a week. Treatment of these transient changes is not indicated. More significant changes in laboratory tests may be followed more closely, if clinically warranted, and may require intervention per irAE guidelines^{102,104} if the changes are associated with clinical symptoms or persistent

Decreased lymphocyte and monocyte counts

Decreases in lymphocyte and monocyte counts are a pharmacodynamic effect of CDX-1140, occurring within 24-48 hours of a dose and typically recovering by 1 week. Decreases in B cells, as determined by flow cytometry, predominates.

Other Adverse Events

Based on a review of the relevant literature and the proposed mechanism of action of CDX-1140 in binding to CD40 expressing cells and enhancing immune reactions, the following additional adverse effects may be encountered:

- Infusion reactions/cytokine release syndrome/hypersensitivity reactions
 - As mentioned above, infusion reactions are likely to occur and may include chills, rigors, fever, rash, nausea, vomiting, myalgias, headache, and hypotension. Obtain serum at the time of an infusion reaction/cytokine release syndrome.
 - As discussed above, patients are to be pre-medicated with antihistamine, acetaminophen, and/or NSAID at least 30 minutes prior to CDX-1140 administrations. Prophylactic premedication with corticosteroids is to be avoided with CDX-1140 because of the potential to attenuate antitumor activity. In the 24 hours following the CDX-1140 infusion, alternate oral acetaminophen (1000 mg) and non-steroidal anti-inflammatory (e.g., ibuprofen 200 mg) q6h. An antihistamine and anti-emetic may also be utilized if clinically indicated.
- Immune-related adverse events (irAEs)

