7.2 DLT Definition

The definition of a dose-limiting toxicity (DLT) will be nearly identical to the definition used in the recent study combining CDX-301 and CDX-1140⁷⁰. A DLT will be defined as any of the following outcomes, attributed to study therapy (including SBRT) and occurring within 8 weeks after initiation of initial study therapy:

- Death
- Any \geq Grade 3 non-hematological toxicity, with the following exceptions:
 - Grade 3 alopecia, vitiligo, or endocrinopathies controlled by hormone replacement therapy
 - Grade 3 nausea that resolves to \leq grade 2 with or without treatment within 72 hours
 - Grade 3 vomiting and diarrhea that resolves to \leq grade 2 with or without treatment within 72 hours
 - Grade 3 fatigue that resolves to \leq grade 2 within 5 days
 - Grade 3 hypertension in the absence of maximal medical therapy
 - Grade 3 adverse event of tumor flare (defined as local pain, irritation, or rash localized at sites of known or suspected tumor) of \leq 7 days in duration
 - Grade 3 amylase or lipase abnormalities that are not associated with symptoms or clinical manifestations of pancreatitis. It is recommended to consult with the Principal Investigator for grade 4 amylase or lipase abnormalities
 - Grade 3 clinically significant laboratory abnormalities that are asymptomatic and can be reversed within 72 hours, however:
 - Any Grade 4 ALT or AST elevation will be a DLT
 - Any Grade 3 ALT or AST elevation that lasts longer than 7 days will be a DLT
 - ALT or AST $> 8 \times$ ULN regardless of duration will be considered a DLT
 - ALT or AST $> 5 \times$ ULN that lasts longer than 14 days will be considered a DLT
 - ALT or AST of $> 3 \times$ ULN with a concurrent total bilirubin $> 2 \times$ ULN will be considered a DLT in the absence of another cause (other than study drug) of these elevations.
- Any of the following hematologic toxicities:
 - Grade 4 anemia (regardless of duration)
 - Grade 4 neutropenia persisting > 5 days
 - Grade 3 thrombocytopenia with hemorrhage
 - Grade 4 thrombocytopenia
 - Any other \geq Grade 3 hematologic adverse event not returning to baseline or \leq grade 1 prior to the next planned study drug dose, excluding asymptomatic lymphopenia which will not be considered a DLT
- \geq Grade 3 infusion reaction
 - Excluding grade 3 infusion reactions resolving within 6 hours with or without treatment

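### Section 8.2 judges safety on a count of DLTs but states its limits and error rates for a Grade 3 or undefined toxicity rate; the figures describe only the DLT rate and should be relabelled and restated

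*Combined protocol and SAP*

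**What the plan says.** Section 8.2 has two DLT criteria. For Phase I, "the study will proceed to Phase II if no more than one out of six subjects on Arm 1 has experienced a DLT". The final criterion, whose counted event is again the DLT, reads: "study therapy will be considered safe and worthy of further study if no more than 4 out of 23 subjects on Arm 1 experience a". In both, the number of Arm 1 subjects with a DLT is the only input.

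The limits follow at once, in other terms: "The target Grade 3 toxicity rate is no more than 12.5%, and a toxicity rate greater than 35% is considered clinically unacceptable". The two operating characteristics are then given for a true toxicity rate. The chance of accepting the treatment "if the true toxicity rate is unacceptably high (>35%) is at most 5"%, and "there is at least an 85% probability of accepting the treatment for further study if the true toxicity rate is less than 12.5"%. None of these sentences uses the term DLT, and *toxicity rate* is not defined.

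Section 7.2 defines the DLT. By default, any Grade 3 or higher non-hematological toxicity attributed to study therapy within 8 weeks of starting initial therapy counts. The exceptions include Grade 3 nausea, vomiting or diarrhea settling within 72 hours, fatigue settling within 5 days, tumor flare of up to 7 days, amylase or lipase changes without pancreatitis, and asymptomatic laboratory changes reversible within 72 hours. For infusion reactions the wording is "Excluding grade 3 infusion reactions resolving within 6 hours with or without treatment". Several Grade 3 hematologic events count only if they persist or, for thrombocytopenia, come with hemorrhage. In the other direction, eye toxicity of Grade 2 that does not improve, and a treatment delay of more than 2 weeks for drug-related toxicity, also count.

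**The concern.** The rule observes one quantity and its limits are worded for another. The only label given to the 12.5% target is Grade 3 toxicity, and the same sentence pairs it with 35%. A reader can easily conclude that the design limits the Grade 3 rate.

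The difference matters for this regimen. Section 5.2.6 lists ten event types seen in more than 10% of CDX-1140 patients, and six of them (fatigue, nausea, diarrhea, vomiting, AST and ALT increase) have some conditional exemption in Section 7.2. On liver tests it says: "The increases are usually low-grade, but can be grade 3, and liver function tests typically return to approach baseline within a week". It also says that immune-related events typically appear several weeks to a few months after treatment starts, so some may fall outside the 8-week window. Repeat cycles (Sections 4.2.2 and 5.2.2) start at least 8 weeks after the first, so toxicity arising from them cannot enter the count.

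At stake is what the final report may claim. A result of 4 or fewer DLTs could be presented as guarding against Grade 3 toxicity above 35%, a rate that the rule does not measure.

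**Working it through.** **Inputs (Section 8.2).** n = 23 Arm 1 subjects; accept if X ≤ 4, where X is the number with a DLT; limits 12.5% and 35%; Phase I gate of at most 1 DLT in the first 6.

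**Step 1. Reproduce the stated figures, taking p as the DLT rate.**
P(accept) = Σ C(23,x) p^x (1−p)^(23−x), x = 0 to 4.
- p = 0.35: 0.00005 + 0.00062 + 0.00365 + 0.01376 + 0.03705 = 0.0551. Stated: at most 5%.
- p = 0.125: 0.04636 + 0.15234 + 0.23939 + 0.23939 + 0.17099 = 0.8485. Stated: at least 85%.

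Both lie close to the stated values, so the plan's numbers evidently come from one binomial on the DLT count. Strictly, each misses its bound slightly (5.5% and 84.8%).

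**Step 2. Require the Phase I gate as well.**
P(accept) = P(0 of 6) × P(at most 4 of 17) + P(1 of 6) × P(at most 3 of 17).
- p = 0.35: 0.0754 × 0.2348 + 0.2437 × 0.1028 = 0.0177 + 0.0250 = 0.0428.
- p = 0.125: 0.4488 × 0.9482 + 0.3847 × 0.8457 = 0.4255 + 0.3253 = 0.7509.

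With the gate the 5% bound is met and the 85% bound is not. Neither version meets both.

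**Step 3. Illustrate what the rule would do for a Grade 3 rate.** Let g be the proportion of subjects with attributable Grade 3 or higher toxicity, and f the share of those subjects who meet the DLT definition. The documents give neither Grade 3 frequencies by event type nor f, so f is an assumption. Assume also that no DLT arises outside this group. The DLT rate is then g × f. With g = 0.35:

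| f | DLT rate | P(accept), rule alone | with gate |
|---|---|---|---|
| 1.0 | 0.350 | 5.5% | 4.3% |
| 0.9 | 0.315 | 10.5% | 8.3% |
| 0.8 | 0.280 | 18.6% | 14.7% |
| 0.7 | 0.245 | 30.2% | 24.4% |
| 0.6 | 0.210 | 45.3% | 37.3% |
| 0.5 | 0.175 | 62.4% | 52.6% |

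The table shows how sensitive the result is to f. It does not estimate the loss of protection in this trial.

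**The case against.** The best reply is that this is loose wording. Section 8.2 is headed Dose-Limiting Toxicity, the preceding sentence sets a DLT rule, and Step 1 shows that the probabilities were computed for the DLT rate. Only the 12.5% figure carries the Grade 3 label; the 35% limit and both probabilities say toxicity rate. Read this way, the binomial calculation is valid for DLTs whatever the Grade 3 rate is. That stands, and it supports the relabelling: the text should name the rate for which the figures hold.

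A reader might go further and infer that Section 7.2 removes most of the expected Grade 3 events, or that the plan's 5% protection has failed by a known amount. The documents support neither:
- Grade 3 non-hematological toxicity is a DLT by default. Most exceptions are limited to brief, asymptomatic or controlled events, and pneumonitis, arthralgia, myalgia and fever have no named exception.
- The list of events above 10% is not broken down by grade.
- Liver tests are only partly exempt. The general laboratory exception needs reversal within 72 hours, while recovery is described as typically within a week. ALT or AST above 8 times ULN counts at any duration.
- f is per subject, so one non-exempt event makes a DLT subject even if other events are exempt. DLTs that are not Grade 3 would offset part of any loss.

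It can also be said that Grade 3 toxicity is watched elsewhere. Section 8.2 reports specific treatment-related events by grade, including delayed ones, and under Section 10.4 the DSMC reviews Grade 3 or higher events every two months and may close accrual. This is real protection during the trial. It does not supply the per-subject proportion with any attributable Grade 3 or higher event, and it does not change what the final rule can conclude.

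**Conclusion.** The terms in Section 8.2 need to be reconciled. The final rule and its probabilities concern the DLT rate as defined in Section 7.2, and the plan states no protection for the overall Grade 3 or higher rate.

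For the DLT rate the size is exact: acceptance is 5.5% at 35% and 84.8% at 12.5%, or 4.3% and 75.1% with the gate, assuming 23 evaluable Arm 1 subjects with independent outcomes. For a Grade 3 rate no figure can be derived; the illustrative range of 10.5% to 62.4% (8.3% to 52.6% with the gate) depends wholly on the assumed 10% to 50% of such subjects not meeting the DLT definition, and on DLTs arising only among them. The point concerns labelling and the scope of the safety claim. It does not show that the DLT definition or the cut-off is wrong.

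**What to change.** In Section 8.2:
1. Replace *Grade 3 toxicity rate* and *toxicity rate* throughout by *DLT rate (Section 7.2, first 8 weeks)*.
2. Restate the operating characteristics as computed for that rate: acceptance probability 5.5% at 35% and 84.8% at 12.5% for at most 4 of 23 alone, or 4.3% and 75.1% if the at-most-1-of-6 gate must also be passed. Say which version applies. Changing the label while keeping the stated 5% and 85% would leave figures that the rule does not give.
3. State that the conclusion *safe* refers to DLTs.
4. Next to the DLT proportion, report the proportion of Arm 1 subjects with any attributable Grade 3 or higher event, with its Clopper-Pearson 95% interval, as a description only. Do not read it against 35%, which becomes a DLT limit under item 1.

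The DLT definition and the 4 of 23 cut-off stay as they are. The cost is a few sentences and one proportion from adverse events already graded by CTCAE (Section 7.1), with no added patients or procedures. The downside is a narrower safety claim and slightly less favourable stated figures.

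### Section 8.2's two safety operating characteristics do not both hold: the final rule alone accepts 5.5% at a 35% DLT rate (stated at most 5%); with the Phase I gate counted, acceptance at 12.5% is 75.1% (stated at least 85%).

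*Combined protocol and SAP*

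**What the plan says.** Section 8.2 contains two rules on DLTs in Arm 1.

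- **Phase I gate:** "the study will proceed to Phase II if no more than one out of six subjects on Arm 1 has experienced a DLT".
- **Final rule, at the end of the trial:** therapy is judged "safe and worthy of further study if no more than 4 out of 23 subjects on Arm 1 experience a DLT".

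After the final rule the section sets two reference rates. The first is worded as a grade: "The target Grade 3 toxicity rate is no more than 12.5" percent. The second is a rate above 35%, which it calls clinically unacceptable. It continues, "This design has the following operating characteristics", and gives two:

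- "The probability of accepting the treatment for further study if the true toxicity rate is unacceptably high (>35%) is at most 5" percent;
- "there is at least an 85% probability of accepting the treatment for further study if the true toxicity rate is less than 12.5" percent.

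If the gate fails, Sections 4.1 and 8.2 have the investigators and the drug supplier review the safety data and "determine if the experimental treatment regimen should be altered". The protocol would then be amended, and a "Phase I component with the new treatment regimen would be added".

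**The concern.** The two probabilities are attributed to the design, and the design in Section 8.2 has two decision points. The text does not say whether the probabilities describe the final rule alone or the gate and final rule together. The distinction matters because a gate can only lower the chance of acceptance. It helps the 5% bound and hurts the 85% one.

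DLT is the Phase I primary endpoint, and these are the only operating characteristics given for its acceptance rule. Someone using them would infer that a regimen at the 12.5% target has at most a 15% chance of being turned away, and that one just above 35% has at most a 5% chance of being accepted. If either inference is wrong, the plan misdescribes the protection its rule gives.

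**Working it through.** **Inputs.** All are from Section 8.2: gate ≤1 of 6; final rule ≤4 of 23; target rate 12.5%; unacceptable rate above 35%; stated acceptance ≤5% and ≥85%. The 23 agrees with Section 4.1 (46 subjects, 1:1, Phase I subjects included). Subjects are treated as independent with a common DLT rate p.

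**Reading 1: final rule alone.** P(accept) = P(X ≤ 4), X ~ Bin(23, p), summing the terms for 0 to 4 DLTs.

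- p = 0.125: 0.0464 + 0.1523 + 0.2394 + 0.2394 + 0.1710 = **0.8485**. This reproduces the stated 85% after rounding.
- p = 0.35: 0.0001 + 0.0006 + 0.0037 + 0.0138 + 0.0371 = **0.0551** (unrounded terms). This does not reproduce the stated 5%.

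Acceptance falls continuously as p rises, so wording the bound for rates above 35% does not rescue it: just above 35% acceptance is still about 5.5%. It reaches 5% at p = 0.3549 and is 4.5% at p = 0.36.

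**Reading 2: gate counted, failed gate taken as non-acceptance.** P(accept) = Σ over x = 0, 1 of P(Bin(6, p) = x) × P(Bin(17, p) ≤ 4 − x), where 17 = 23 − 6.

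- p = 0.125: 0.4488 × 0.9482 + 0.3847 × 0.8457 = 0.4255 + 0.3253 = **0.7509** (unrounded terms).
- p = 0.35: 0.0754 × 0.2348 + 0.2437 × 0.1028 = 0.0177 + 0.0251 = **0.0428**.

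Here the 85% level is reached only at p = 0.0984 or below. The gate by itself passes 0.4488 + 0.3847 = 0.8335 at 12.5%, already below 85%.

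| | Stated | Final rule alone | Gate and final rule |
|---|---|---|---|
| Acceptance at 12.5% | ≥85% | 84.8% | 75.1% |
| Acceptance at 35% | ≤5% | 5.5% | 4.3% |

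**Why the readings differ at 12.5%.** The gap is 0.8485 − 0.7509 = 0.0976. It is the chance of failing the gate when the same regimen, carried on to 23 subjects, would have shown at most 4 DLTs. Gate results of 2, 3 and 4 DLTs contribute 0.0881, 0.0093 and 0.0003. Almost all of the gap is therefore the single outcome of 2 in 6.

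**Other routes to the stated pair.** None of the following gives both ≤5% and ≥85%:

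- normal approximation, with or without continuity correction, or Poisson;
- 22 or 24 subjects;
- cut-offs of 3 or 5;
- conditioning on passing the gate;
- counting only the 17 later subjects.

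Simulation agreed with the exact results for both readings.

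**The case against.** The strongest reply is that the final-rule reading is plainly the intended one. The probabilities follow the ≤4 of 23 rule in the same paragraph and repeat its language about further study. The gate sits in an earlier paragraph and decides only whether Phase II opens. On that reading the 85% statement is right after rounding, and the 5% bound fails only for rates from 35% to about 35.5%. That is half a percentage point.

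The second part of the reply is that 75.1% rests on an assumption the plan does not make. Failing the gate leads to a review and a judgement, not to rejection, and continuing the same regimen is not expressly excluded.

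Most of this stands. The final-rule reading is the more natural, and the error there changes no decision. Reading 2 is conditional, and no probability can be attached to what a review would decide. Two things remain:

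- The bound is written as a maximum, and 5.5% exceeds it on the reading most favourable to the plan.
- The figures are attributed to the design as a whole, in a section that opens with the gate as a safety stopping rule. The text after a failed gate speaks of a new regimen, which supports treating the tested one as not accepted. A reader can reasonably take the figures to cover both rules.

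**Conclusion.** The statement is wrong as written. On the final rule alone, the 5% bound is missed by 0.5 point at 35%, and the 85% figure stands. With the gate counted, the 5% bound holds and the 85% figure is missed by about 10 points. A regimen at the 12.5% target would then have about a 25% chance (1 − 0.7509) of not being accepted as tested, against the 15% the text implies.

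The first result needs only the binomial model. The second also needs a failed gate to be regarded as non-acceptance, which Sections 4.1 and 8.2 support but do not state. The effect is on how the rule is described. Section 10.4 has the DSMC review all Phase I safety data before Phase II, and that oversight is unaffected.

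A separate wording point, on which this conclusion does not rest: the 12.5% target is expressed as a Grade 3 toxicity rate, while both rules count DLTs. The two are not the same under Section 7.2, which leaves out several Grade 3 events and includes outcomes not defined by Grade 3, such as persistent grade 2 eye pain and a treatment delay of more than 2 weeks. The calculations here take both reference rates as DLT rates.

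**What to change.** Replace the two operating-characteristic sentences in Section 8.2 with text such as:

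> For the final rule alone (≤4/23), the probability of acceptance is 84.8% at a true DLT rate of 12.5% and 5.5% at 35%. If the Phase I gate (≤1/6) is also counted, and a regimen that fails the gate is regarded, for this calculation only, as not accepted, the probabilities are 75.1% and 4.3%.

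The sponsor should also confirm that the 12.5% target refers to the DLT rate, and word it so.

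The cost is an edit to Section 8.2. No decision rule, sample size or procedure changes. The downside is that the printed figures become less favourable.
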